8. DATABASE AND REGISTRATION

8.1 Creating and implementing a database

An external group will be hired to create and implement a database.

8.2 Database features.

It contains all the fields contemplated in the CRD in the specific format for each one according to the type of data obtained.

Allow online data entry.

Access by multiple users as long as a username and password are available.

Access will be possible both from the computers of the participating hospitals and from an external computer.

You will have appropriate systems in place to maintain data integrity.

Backups can be made repeatedly to avoid data loss.

The data from the fields can be obtained to be analyzed by the statistical program IBM SPSS26 Statistics and R software.

Hosting of said database will be requested for a period of more than one year.

8.3 Data registration, authorizations and database control

- . Access with username and password.
- . Only the following will have access to the database: the principal investigator, authorized study collaborators, the person carrying out the statistical studies, the study coordinator in charge of monitoring the study.

- . The data will be entered by: researchers and study coordinator.
- . The data will be controlled and corrected if necessary by the study coordinator.
- The company hired to prepare it will take care of maintenance, security and that backup copies are made regularly.

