a) This study also aims to control the effects that said drug may have on the calcium level of the monitored individuals. Calcitriol supplementation is considered safe since the recommended doses are well known. However, it is necessary to control the effects that such supplementation may have on the calcium level of Friedreich's ataxia patients.

b) Analyze the effect of calcitriol administration on frataxin levels and other biochemical parameters in platelets obtained from the patients under study. Frataxin is undetectable in serum or plasma, while its detection in blood is not recommended for the objectives of the project, since it is present in erythrocytes which have a high half-life (around 115 days). This could make it difficult to observe changes in frataxin content due to the treatments carried out. Therefore, its platelet content will be analyzed, since these have a half-life of 10 days. Platelets can be easily obtained from

circulating blood and contain active mitochondria that sustain most of their ATP production. Various mitochondrial proteins will also be quantified throughout the study and the effect of calcitriol on their production.

c) Effect of treatment with calcitriol on activities of daily living with the Barthel Index and quality of life using the SF36 questionnaire, at the beginning and at the end of treatment.

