The present study is a pilot study aimed at verifying the effects of treatment with calcitriol on neurological function, calcium levels, frataxin levels, and quality of life in patients with FA.

This is an open study, all patients will receive treatment, and the results obtained before and after treatment will be compared, using parameterized tests and video filming.

3.3 Description of trial treatment.

The drug used, calcitriol, is on the market under the registered trademark Rocaltrol®. The lowest dose will be used: 25 micrograms, orally once a day for one year (Rocaltrol 0.25 micrograms soft capsules, presented in a PVC blister containing 20 capsules).

3.4 Expected duration of participation and all trial periods.

The study will continue over one year.

It will begin with a recruitment period, a screening period that includes the evaluation of inclusion and exclusion criteria, the assessment of neurological function, a determination of calcium, vitamin D, kidney function, albumin, proteins, sodium, potassium, phosphate, and pregnancy test in pre-menopausal women, and extraction for basal determination of frataxin, evaluation of the quality of life questionnaire. An ECG will also be performed.

The treatment period will begin from here.

Fifteen days after the start of this, the next visit will be carried out with the first extraction for determination of frataxin, calcium, kidney function, sodium, potassium, phosphate, ECG and assessment of possible symptoms related to possible adverse effects of the treatment.

This procedure will be repeated at 4, 8 and 12 months with determination of frataxin, calcium, albumin, kidney function, ECG and assessment of possible symptoms related to possible adverse effects of the treatment (Addendum 6).

After 6 months of treatment, the first assessment of neurological function will be carried out.

At the last visit of the 12 months, a new assessment of neurological function, Barthel index and final quality of life questionnaire will also be carried out (Addendum 5.1, Addendum 5.2, Addendum 5.3 and Addendum 5.4).

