6. ASSESSMENT OF EFFICACY

6.1 Specification of efficacy variables.

The efficacy variables for improving neurological function would be the initial, intermediate and final comparison of:

- Partial and total values of the SARA scale (Scale for the assessment and grading of cerebellar function in ataxias).
- SCAFI index (composite Z-score) result of the transformation of the results of:
 - .. Average time to travel 8 meters round trip.
 - .. Time spent completing the 9-hole test with dominant and non-dominant hands.
 - .. Number of syllables PA-TA repeated in two series of 10 seconds.
- Total partial scores of the Barthel Index.
- Total score and each dimension of the SF36 quality scale.
- Increase in frataxin levels compared to baseline measurement figures.
- Significant change in the values of the mitochondrial proteins studied.

6.2 Methods and schedule for evaluation, registration and analysis of efficacy parameters.

- Evaluations of efficacy parameters will be carried out at the beginning, after 6 months and after one year of treatment for neurological function. The quality of life questionnaire and the Barthel index will be administered at the screening visit and after one year of treatment.
- The registration of these data will be carried out in the corresponding CRD.

- The parameters will be assessed and compared at the end of the study.

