9.2 Statistics methods

A descriptive analysis will be carried out using the usual statistics: mean and standard deviation, or median and interquartile range for quantitative variables with non-normal distribution. The normality of the data will be checked using the Shapiro-Wilks test and/or Q-Q plots. The qualitative variables will be described according to the number and percentage of subjects in each category.

The effect of treatment with calcitriol on neurological function will be evaluated using a mixed linear model with the levels of neurological function tests as a dependent variable and the measurement time (screening, 6-month control and final control) as an independent variable included as an effect. random. To take into account possible confounding effects, covariates will be introduced as fixed effects. The same analysis will be repeated for frataxin levels and other biochemical parameters in platelets.

Comparison of baseline frataxin levels between healthy controls and patients with ataxia will be carried out using the Student's t test for independent data or the Mann-Whitney U test, if the data do not meet the assumption of normality. The relationship between the increase in frataxin production and clinical improvement will be

evaluated using a logistic regression model where the dependent variable will be defined dichotomously by jointly evaluating frataxin levels against increases of more than one point on the scale. SARA, two or more points of the SCAFI composite index (which would add the results of the 8 m walk test, time taken from the 9-HPT, the number of syllables from the PATA test), the values of the Barthel Index in 10% and the SF36 questionnaire by 20% on the values obtained in the first evaluation.

The results will be expressed in odds ratio (OR).

The effect of treatment with calcitriol on the quality of life of the patients at the beginning and end of treatment will be evaluated through the t-student test for paired data or the Wilcoxon test, if normality is not met in the distribution of the data.

To assess toxicities, a table of frequencies of occurrences will be created.

Statistical analysis will be performed with o IBM SPSS Statistics version 26 and R software.

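### Nothing in the plan keeps a patient's interim frataxin results from whoever scores SARA, although the frataxin-clinical association is a planned analysis

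*Combined protocol and SAP*

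**What the plan says.** Section 3.2 sets the masking: "This is an open study, all patients will receive treatment". No section describes masked or independent scoring. Section 3 has the neurological tests filmed and the files archived, but specifies no masked reading of them.

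Section 6.1 places "Increase in frataxin levels compared to baseline measurement figures" and change in the mitochondrial proteins in the same list as SARA, SCAFI, Barthel and SF36. Section 2.2 b adds: "Various mitochondrial proteins will also be quantified throughout the study". Section 6.2, which covers the efficacy parameters, states: "The registration of these data will be carried out in the corresponding CRD". Section 8.2 says of the database: "It contains all the fields contemplated in the CRD".

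Section 8.3 gives the access rule: "Only the following will have access to the database: the principal investigator, authorized study collaborators, the person carrying out the statistical studies", together with the study coordinator. On entry it says: "The data will be entered by: researchers and study coordinator". It separates no fields and no roles.

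Section 9.2 makes the link between the two kinds of measurement a planned analysis. The sentence begins "The relationship between the increase in frataxin production and clinical improvement will be" and goes on to a logistic regression reported as an odds ratio.

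**The concern.** In an open single-group study, knowing that a patient is treated applies to everyone. It can shift all scores, but it cannot by itself make the scores follow frataxin. Knowing each patient's frataxin result is different, because that information varies between patients. The rationale in section 1 is that raising frataxin could reverse manifestations of the disease. A rater who holds that view and knows who has responded may score the responders a little better. That would produce an association with no biological link behind it. Masking a video reader to visit alone would not remove it.

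At stake is the analysis in section 9.2 that would connect the laboratory effect to clinical change. It is informative only if the two measurements are made independently, and the plan contains no rule that keeps them so.

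**Working it through.** **Sampling against scoring.** Sections 3 and 3.4 put frataxin sampling at baseline, 15 days, 4, 8 and 12 months, and neurological scoring at baseline, 6 and 12 months. The budget in section 11.2 agrees with this: 20 patients × 5 samples = 100, plus 20 heterozygotes and 20 healthy controls = 140 determinations, as stated.

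| Scoring | On-treatment frataxin samples already drawn | Count |
|---|---|---|
| 6 months | 15 days, 4 months | 2 |
| 12 months | 15 days, 4 months, 8 months | 3 |

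The 12-month sample is drawn at the final scoring visit, so it is not counted.

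**What would have to be true for bias.** (a) Frataxin results are in the shared record or otherwise disclosed. (b) The scorer is among those who can see them. (c) They are back before scoring. Read together, sections 6.1, 6.2 and 8.2 point to (a). Section 8.3 allows (b) without stating it. The plan is silent on (c). No section excludes any of the three.

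**Number of patients for the illustration.** Section 9.1 gives a two-arm pilot total of 24-40, a single-group factor of 0.5 and 20% loss: 24 × 0.5 / 0.8 = 15 and 40 × 0.5 / 0.8 = 25, which reproduces its range of 15-25. With 20 planned and 20% lost, 20 × 0.8 = 16 complete.

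**Illustration.** The documents give no SD for SARA change and no rater effect, so both are assumed. Let k be the standardised frataxin change known to the rater and f the standardised change that is analysed, with correlation ρ between them. The recorded change in favour of improvement is y = SD × e + b × k, where e is standard normal and there is no true link. The population correlation between y and f is then ρ × b / √(SD² + b²). For SD 1.5, b = 1 and ρ = 0.7, this is 0.7 × 1 / √3.25 = 0.39.

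Simulated two-sided 5% Pearson test, n = 16. In each cell the lower figure is for SD 3 and the higher for SD 1.5:

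| Shift b (points per SD of known frataxin change) | ρ = 0.5 | ρ = 0.7 | ρ = 1 |
|---|---|---|---|
| 0 | about 5% | about 5% | about 5% |
| 0.5 | 6-9% | 7-13% | 9-22% |
| 1 | 9-18% | 13-33% | 22-65% |

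The ρ = 1 column is an upper case. The 12-month value cannot be known from an earlier draw, so a change analysed to 12 months is only partly known to the rater.

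A second form has 20 patients, half of them known to the rater as frataxin risers, and a t test of SARA change between the halves. It gives 6-11% for a 0.5-point shift and 11-29% for a 1-point shift over the same SD range. The direction is the same and the values are moderate.

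**The case against.** The strongest reply is that the route to bias rests on silence at three points.

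- **Where frataxin is held.** In section 6.2 the registration sentence follows scheduling text that covers only neurological function, SF36 and Barthel. Section 7.2, which registers the safety tests, omits frataxin as well. The CRD is not in the documents. This stands as an ambiguity. Still, section 6.2 is headed as covering the efficacy parameters, and section 6.1 counts frataxin and the proteins among them.
- **Who scores and when results return.** The documents do not say. The assays are run at a separate institute, and €250 for shipping against 140 determinations (250 / 140 = about €1.8 each) is compatible with batching. Section 6.2 puts comparison at the end of the study. This also stands, but a late comparison does not delay assay, entry or viewing, and if batching is intended the plan does not say so.
- **Size and importance.** The simulation is not the planned analysis. Section 9.2 builds frataxin into a joint dichotomous outcome with SARA, SCAFI, Barthel and SF36, and specifies no correlation test. The association is not among the objectives in section 2, frataxin is a secondary variable, and this is a pilot. The walk, peg and PATA tests are timed or counted, so SARA is the most exposed measure. Filming leaves masked re-scoring possible. All of this stands, and it limits the weight of the point.

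A reader might infer that the raters themselves fill in and read the database and will know frataxin before they score, or that patients will be told their results. The documents support neither. They show only that nothing prevents it.

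**Conclusion.** The point holds as a missing safeguard. The plan does not name the raters, does not mask them to frataxin, does not say when laboratory results return, and gives access without field limits. Prior knowledge of the 15-day, 4-month and 8-month results is therefore not ruled out, and such knowledge could bias the association in section 9.2.

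The documents do not allow the size to be derived. Under the assumptions stated, the false-positive rate goes from 5% to about 6-33% with partial knowledge (ρ 0.5 to 0.7) and to about 9-65% with full knowledge. These figures show that the mechanism could matter in a sample this small. They should not be read as error rates of the planned logistic model or as a prediction for this trial. The change is worth making because it is cheap, with medium confidence that the exposure would arise in practice.

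**What to change.** Add to section 8.3:

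> Frataxin and mitochondrial protein results are held by the laboratory in a separate controlled file. They are not entered in the shared database or disclosed to the neurological raters, clinical investigators or patients until the last patient's 12-month neurological, Barthel and SF36 data are entered and locked. The statistician then merges the files.

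Calcium, kidney function and ECG results stay visible to the clinicians as now. No withdrawal or safety rule in sections 4.4, 5.4 or 7 uses frataxin, so holding it back affects no decision that the plan describes during treatment.

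The cost is a second controlled file, a late merge, and a delay until then in the coordinator's checking of these results.

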9. STATISTICS

9.1 Sample size for a pilot study.

Number of subjects planned: 20

Given the type of study design, a formal calculation of the sample size is not required.

However, general rules for determining the appropriate sample size for a pilot study have been described in the scientific literature. For two-arm studies, it is recommended to recruit between 24-40 patients in total. For single-group studies, the calculation can be adapted by applying an adjustment factor of 0.5. Therefore, in our study it is estimated that it will be necessary to recruit a minimum of between 15-25 patients, assuming a loss rate of 20%.

9.2 Statistics methods

A descriptive analysis will be carried out using the usual statistics: mean and standard deviation, or median and interquartile range for quantitative variables with non-normal distribution. The normality of the data will be checked using the Shapiro-Wilks test and/or Q-Q plots. The qualitative variables will be described according to the number and percentage of subjects in each category.

The effect of treatment with calcitriol on neurological function will be evaluated using a mixed linear model with the levels of neurological function tests as a dependent variable and the measurement time (screening, 6-month control and final control) as an independent variable included as an effect. random. To take into account possible confounding effects, covariates will be introduced as fixed effects. The same analysis will be repeated for frataxin levels and other biochemical parameters in platelets.

Comparison of baseline frataxin levels between healthy controls and patients with ataxia will be carried out using the Student's t test for independent data or the Mann-Whitney U test, if the data do not meet the assumption of normality. The relationship between the increase in frataxin production and clinical improvement will be

evaluated using a logistic regression model where the dependent variable will be defined dichotomously by jointly evaluating frataxin levels against increases of more than one point on the scale. SARA, two or more points of the SCAFI composite index (which would add the results of the 8 m walk test, time taken from the 9-HPT, the number of syllables from the PATA test), the values of the Barthel Index in 10% and the SF36 questionnaire by 20% on the values obtained in the first evaluation.

The results will be expressed in odds ratio (OR).

The effect of treatment with calcitriol on the quality of life of the patients at the beginning and end of treatment will be evaluated through the t-student test for paired data or the Wilcoxon test, if normality is not met in the distribution of the data.

To assess toxicities, a table of frequencies of occurrences will be created.

Statistical analysis will be performed with o IBM SPSS Statistics version 26 and R software.

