4. SELECTION AND WITHDRAWAL OF SUBJECTS

Patient recruitment will be proposed to patients with FA controlled in the Ataxia Unit of the joint Neurology service of the [name] University Hospital and the Santa Caterina Hospital who meet the inclusion criteria and lack exclusion criteria and wish to participate in the study. To reach the desired "n" (20 patients), an invitation to participate will be made through a press release on the websites and publications of

FEDAES (Federation of Ataxias of Spain) and ACAH (Catalan Association of Hereditary Ataxias) (Addendum 2). This invitation will include: the title of the study, description of the objectives, duration of the research, contact email address from which more detailed information will be sent to those interested in participating. The information will be expanded by letter/mail (Addendum 3) to those who request to participate and they will be scheduled for the screening visit.

4.1 Inclusion criteria.

In the screening visit, the inclusion criteria will be assessed:

Patients with FA confirmed by molecular genetic studies, who are between 16 and 65 years old and maintain the ability to walk, even with external support of any type.

4.2 Exclusion criteria.

During the screening visit, a first blood draw will be carried out to assess frataxin levels and a determination of calcium, albumin, glomerular function, vitamin D, sodium, potassium and phosphorus. Patients with hypercalcemia, or impaired glomerular function or elevated creatinine levels will be excluded. A pregnancy test will be carried out in pre-menopausal women.

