4.3. Participation of heterozygotes and healthy subjects

In order to verify the effectiveness of treatment with calcitriol, it is essential to have the levels of frataxin in two situations, firstly, that of healthy controls who do not carry the AF mutation, and secondly, the levels presented by heterozygous individuals. . It is known that the latter have intermediate figures in frataxin levels: higher than those of affected individuals, but lower than those of the population that does not carry the mutation. Heterozygotes are free of FA symptoms and do not present any alterations; in them, although reduced, the amount of protein is sufficient to keep them asymptomatic throughout their lives. It would therefore be a hypothetical ideal level to approach in order to reach a situation close to clinical normality.

Therefore, we will proceed to draw blood to determine levels of frataxin and mitochondrial proteins in these people. Determinations will therefore be carried out either in parents of those affected or in known heterozygous siblings.

The same determinations will be carried out on healthy controls, who, in theory, do not carry the mutation (the conditions of the study do not allow us to verify the presence of the mutation in this group). The prevalence of the FA mutation in the general population is 1/100).

In these determinations, the levels of frataxin and mitochondrial proteins will be assessed. The data obtained will allow a comparative study between the values of healthy individuals, heterozygotes, and those affected by FA, and in these their basal levels and those obtained during treatment with calcitriol.

Therefore, the following will be chosen for each patient included in the study:

- A healthy control heterozygous for FA, choosing the volunteer parent who attends the screening visit or, if possible, a heterozygous sibling. It will be verified that the heterozygous healthy control does not have any neurological disease, nor any disease related to the metabolism of calcium or Vitamin D and that it is not being treated with Calcium or Vitamin D.

- A non-familial healthy control and therefore supposedly not heterozygous for FA (n=20). You must not have any neurological disease, any disease related to calcium or vitamin D metabolism and you must not be under treatment with calcium or vitamin D.

Once the healthy controls have been chosen, blood will be drawn, after signing the specific informed consent for this type of collaboration.

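### The frataxin reference groups have no stated age or sex matching and the baseline comparison is unadjusted, so differences from them may partly reflect age or sex

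*Combined protocol and SAP*

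**What the plan says.** Section 4.3 calls for frataxin levels in two reference groups. It regards them as essential for verifying that calcitriol works, and it treats the heterozygote level as a notional target for patients.

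- **Heterozygotes.** Determinations are made "either in parents of those affected or in known heterozygous siblings". For each patient one is taken, "choosing the volunteer parent who attends the screening visit or, if possible, a heterozygous sibling".
- **Unrelated controls.** One per patient: "A non-familial healthy control and therefore supposedly not heterozygous for FA (n=20". Their conditions are "You must not have any neurological disease, any disease related to calcium or vitamin D metabolism", and no treatment with calcium or vitamin D. The heterozygotes have the same kind of conditions.
- **Patients.** Under 4.1 they are those "who are between 16 and 65 years old and maintain the ability to walk".

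No age range, sex balance or matching rule is stated for either reference group.

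For analysis, 9.2 specifies "Comparison of baseline frataxin levels between healthy controls and patients with ataxia", by "Student's t test for independent data or the Mann-Whitney U test, if the data do not meet the assumption of normality". Covariates are mentioned in 9.2 only for the mixed model on measurement time, and they are not named. Section 4.3 announces a comparison of healthy, heterozygous and affected people, but 9.2 names no method for three groups.

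**The concern.** A comparison between genotype groups is observational. If the groups differ in age or sex, and platelet frataxin varies with either, an unadjusted test attributes that variation to genotype. Two features leave room for this. A parent is necessarily older than the patient, and the parent's sex depends on who attends. The unrelated volunteers may differ from the patients in age or sex because nothing in 4.3 prevents it. Section 9.2 provides for confounding in the longitudinal model, which follows the same patients over time, but not in the between-group comparison, where age and sex imbalance matters more.

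At stake is the position of the benchmark. If frataxin falls with age, a level taken from older relatives is too low and patients look closer to the target than they are. If it rises with age, they look further away.

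**Working it through.** **Group sizes.** Section 9.1 gives "Number of subjects planned: 20" and a range of 15–25. This reproduces: 24 × 0.5 = 12 and 12/0.8 = 15; 40 × 0.5 = 20 and 20/0.8 = 25. The 140 frataxin determinations in section 11.2 fit 20 people per reference group: 20 patients × 5 samplings (screening, 15 days, 4, 8 and 12 months) + 20 + 20 = 140. The plan gives no power, alpha or standard deviation (SD) for the control–patient comparison. At 20 versus 20 and an assumed two-sided alpha of 0.05, a t test has 80% power for a difference of 0.91 SD.

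**Shift in percent.** Every slope here is an assumption. Shift = change per year × age gap × share of heterozygotes who are parents.

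- No age effect: 0%.
- All parents: 0.3% × 25 = 7.5%, up to 1% × 30 = 30%.
- Half parents: 7.5%/2 = 3.75%, up to 30%/2 = 15%.
- All siblings: about 0%.

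For scale, section 1.2 cites another drug that raises frataxin by 50%, and section 1 credits calcitriol with up to 2.5 to 3 times.

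**Shift in SD units.** A simulation (3,000 runs per setting, 20 versus 20, no true genotype effect) assumed patient ages uniform on 16–65, parents 28 years older, sibling age differences with SD 4 years, and independent errors. The expected unadjusted shift is slope per decade × 2.8 × parent share; for example, 0.2 × 2.8 × 1 = 0.56.

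| Parent share | Slope (SD per decade) | Unadjusted shift (SD) | Unadjusted rejection at 5% | Standard error (SE), unadjusted | SE, age-adjusted |
|---|---|---|---|---|---|
| All | 0 | 0 | 5% | 0.31 | 0.45 |
| All | 0.1 / 0.2 / 0.3 | 0.28 / 0.56 / 0.84 | 14% / 39% / 68% | 0.32 / 0.33 / 0.34 | 0.45 |
| Half | 0.1 / 0.2 / 0.3 | 0.14 / 0.28 / 0.42 | 6% / 13% / 20% | 0.32 / 0.33 / 0.35 | 0.34 |
| None | 0.1 / 0.2 / 0.3 | about 0 | 3–5% | 0.32 / 0.33 / 0.34 | 0.31–0.32 |

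Age adjustment brings the shift to about 0 and the rejection rate to about 5% throughout. Its cost can be checked by hand for the all-parent case. The SD of a uniform age on 16–65 is 49/√12 = 14.1 years, or 1.41 decades. The within-group sum of squares is about 2 × 19 × 2.00 = 76. The SE is therefore √(2/20 + 2.8²/76) = √(0.100 + 0.103) = 0.45 SD.

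**Unrelated controls.** No age gap is built in. Each 10-year difference in mean age would shift the comparison by 0.1 to 0.3 SD at the same assumed slopes.

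**Sex.** Shift = imbalance × sex effect. With an imbalance of 25 to 50 percentage points and an assumed effect of 0.3 to 0.5 SD, this runs from 0.25 × 0.3 = 0.075 to 0.5 × 0.5 = 0.25 SD.

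**The case against.** Four points tell against a stronger reading, and each stands.

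- A reader might infer that the heterozygote level comes from people a generation older. The text does not support that: 4.3 names siblings twice, and its wording can be read as already favouring them. The gap applies only to the share who are parents, which is not stated.
- A reader might infer that the t test in 9.2 sets parents against patients. It refers to healthy controls, while 4.3 uses that term both for non-carriers and, later, for heterozygotes. If only the unrelated volunteers are meant, that test contains no parental age gap. What is then missing is any named method for the heterozygote comparison.
- A reader might infer that the group differences do mix genotype with age and sex. That requires platelet frataxin to vary with age or sex. No section says that it does, and with no dependence there is no bias in any scenario.
- A reader might infer that the efficacy conclusions are compromised. The primary variables in 3.1 are neurological tests. Frataxin efficacy in 6.1 is change from each patient's own baseline. No success or continuation rule uses the reference levels.

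The rejection rates above also assume no genotype effect, whereas 4.3 takes as known that patients are lowest and heterozygotes intermediate. A spurious genotype difference is therefore not the realistic harm; a misplaced benchmark is. Finally, age adjustment is weakest where it is most wanted, in an all-parent group.

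None of this supplies the missing selection criterion or the missing adjustment.

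**Conclusion.** The point holds as a modest, inexpensive improvement. Neither reference group has a stated age or sex criterion and the planned test has no covariates, so differences from the reference levels may partly reflect age or sex. The shift may be zero. At the assumed slopes it reaches 0.28 to 0.84 SD if every heterozygote is a parent, half that if half are, and about nothing if all are siblings. These figures rest on assumed slopes, sex effects and age gaps, since the documents give no frataxin SD and no age or sex effect. The consequence is confined to how on-treatment frataxin is read against the heterozygote and non-carrier levels.

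**What to change.** In 4.3, choose each unrelated control of the same sex as the patient and of similar age, for example within 5 years. Record age, sex and parent or sibling status for all controls. The sibling option is already there and needs no change.

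In 9.2, replace the unadjusted test with a linear model of frataxin, preferably on the log scale, on three groups (patient, heterozygote, non-carrier). Include age and sex as covariates and allow for the patient–relative link, for example with a random family effect. This also supplies a method for the three-group comparison that 4.3 announces and makes clear where the heterozygotes belong.

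The cost is a few demographic fields, a change of wording, and slightly more care in choosing volunteers. No subjects or samples are added, and the 140 determinations stand. Matching has to be settled before the volunteers are sampled; adjustment can still be specified afterwards. The statistical price is precision: if all heterozygotes are parents, the standard error of their contrast with patients rises from about 0.31–0.34 to 0.45 SD under the assumptions above. If most are parents, report that imprecision alongside the benchmark.
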